The study allows the opportunity to expand understanding of W-SUDs' performance among this population whilst contributing to our overall understanding of Covid-19's impact upon this population. When Covid-19 spread, users from around the world came to Woebot to discuss the pandemic and seek help. The company responded by building a Covid-19 specific program for Woebot (W-C19) which was initially deployed in March 2020. Elements of our W-C19 program have already been integrated into W-SUDs because we felt that it was timely and appropriate to address users' concerns about the pandemic and demonstrated that Woebot was 'intelligent' to the current crisis.

The proposed supplement will offer immediate access to a digital therapeutic in a resource constrained, socially distanced healthcare ecosystem to an already vulnerable and underserved population, who are likely faced with readily growing psychological challenges.

11. Privacy and Confidentiality

Title : Woebot for Substance Use Disorders during COVID-19 (SU sIRB)
Approval Period: 04/30/2022 - 04/30/2023

Privacy Protections

a) Describe how the conditions under which interactions will occur are adequate to protect the privacy interests of participants (e.g., privacy of physical setting for interviews or data collection, protections for follow-up interactions such as telephone, email and mail communications).

All assessments, including the screening and the two assessment batteries, will be administered via a HIPAA compliant survey administration tool commonly used by Stanford University in its clinical trials (Qualtrics or REDCap). Given the high data protection safeguards embedded within Qualtrics and REDCap, there is little risk to the subject associated in regards to their privacy and/or confidentiality.

Research material obtained from human subjects will involve behavioral and psychological assessments including self-report questionnaires. All data will be obtained specifically for purposes of this research project. Data that is obtained from the Qualtrics or REDCap assessments will be stored and protected within Qualtrics or REDCap. Data that is obtained via Woebot will be encrypted and stored on Amazon Web Services (AWS); Woebot Labs data gathering and storage procedures are compliant with both the Health Insurance Portability and Accountability Act (HIPAA) and the European Union's General Data Protection Regulation (GDPR) compliant. Only members of the research team (PI, Co-PIs, biostatistician, research assistant) will have access to the data.

Confidentiality Protections

b) Specify PHI (Protected Health Information). PHI is health information linked to HIPAA identifiers (see above). List BOTH health information AND HIPAA identifiers. If you are using STARR, use the Data Privacy Attestation to ensure that your request will match your IRB-approved protocol. Be consistent with information entered in section 15a.

Individual names, email addresses, phone numbers, dates of birth, gender/biological sex, IP addresses (automatically collected through Qualtrics), geo location (automatically collected through Qualtrics), and zip codes.

Drug Use Psychopathology

1. The Drug Abuse Screening Test 10 (DAST-10), a brief, 10-item self-report measure adapted from the 28-item DAST, assesses consequences related to drug abuse, excluding alcohol and tobacco. A score of 3 or higher indicates significant problems related to drug abuse. The DAST-10 demonstrated discriminant validity between individuals (i) with lifetime drug use disorders and those without and (ii) who are current abusers and those who are former abusers. It also has moderate level of test-retest and reliability as well as sensitivity and specificity.
2. The Alcohol Use Disorders Identification Test-Consumption (AUDIT-C) is a widely used 3-item self-report screen for hazardous or harmful alcohol consumption that is based off of the 10-item original AUDIT. Developed by the World Health Organization, the AUDIT has been tested extensively in primary-care settings and various outpatient substance abuse treatment population, supporting the application of this screener tool. The AUDIT-C has been tested and validated across racial groups.
6. The Drug Abstinence Self-Efficacy Scale (DASE) is a 12-item self-report scale, reflecting Bandura's (1986) cognitive-behavioral

Title : Woebot for Substance Use Disorders during COVID-19 (SU sIRB)

Approval Period: 04/30/2022 - 04/30/2023

self-efficacy theory, and is a shortened version of the original 20-item scale. The 20-item scale has shown to be a reliable and valid measure of self-efficacy for drug use. The scale will be adapted to refer to use of both drugs and alcohol, by including that language in the item stem.

General Psychopathology

3. The Patient Health Questionnaire (PHQ-9) is a brief 9-item scale used to determine the severity of depression in medical populations. The PHQ-9 has high reliability across populations. We will not include item #9 that assesses suicidal ideation.

4. The Generalized Anxiety Disorder (GAD-7) is a brief self-report scale that identifies the degree to which an individual may have generalized anxiety disorder. This scale has good internal consistency, convergent validity with depression, stress, and anxiety, and is a valid and efficient tool for GAD screening in clinical and general populations.

Employee Health

5. The CAGE Adapted to Include Drug USE (CAGE-AID) was developed by the John Hopkins Dept of Medicine. It's a brief instrument to measure problematic drug use. The CAGE-AID is designed to be an easy yet effective way for primary care providers to determine if substance abuse exists and needs to be addressed.

7. The Michigan Alcohol Screening Test (MAST), revised is a 22 question instrument to measure problematic alcohol use. One of the most widely used measures for assessing alcohol abuse, the MAST is a questionnaire designed to provide a rapid and effective screening for lifetime alcohol-related problems and alcoholism. The MAST has been productively used in a variety of settings with varied populations.

8. The Short Inventory of Problems- Alcohol and Drugs (SIP-AD) is a clinically tested 15-item measure developed by NIH funded research that assesses severity of problematic drinking and drug usage.

c) **You are required to comply with University Policy that states that ALL electronic devices: computers (laptops and desktops; OFFICE or HOME); smart phones; tablets; external hard disks, USB drives, etc. that may hold identifiable participant data will be password protected, backed up, and encrypted. See <http://med.stanford.edu/datasecurity/> for more information on the Data Security Policy and links to encrypt your devices.**

Provide any additional information on ALL data security measures you are taking. You must use secure databases such as <https://researchcompliance.stanford.edu/panels/hs/redcap> RedCap. If you are unsure of the security of the system, check with your Department IT representative. Please see <http://med.stanford.edu/irt/security/> for more information on IRT Information Security Services and http://www.stanford.edu/group/security/securecomputing/mobile_devices.html for more information for securing mobile computing devices. Additionally, any PHI data on paper must be secured in an locked environment.

By checking this box, You affirm the aforementioned. Y

All assessments, including the screening and two assessment batteries, will be administered via a HIPAA compliant survey administration tool commonly used by Stanford University in its clinical trials (Qualtrics or REDCap). Given the high data protection safeguards embedded within Qualtrics, there is little risk to the subject associated in regards to their privacy and/or confidentiality.

Research material obtained from human subjects will involve behavioral and psychological assessments including self-report questionnaires. All data will be obtained specifically for purposes of this research project. Data that is obtained from the Qualtrics or REDCap assessments

Title : Woebot for Substance Use Disorders during COVID-19 (SU sIRB)
Approval Period: 04/30/2022 - 04/30/2023

will be stored and protected within Qualtrics or REDCap, and on Stanford Medicine Box. Data that is obtained via Woebot will be encrypted and stored on Amazon Web Services (AWS); Woebot Labs data gathering and storage procedures are compliant with both the Health Insurance Portability and Accountability Act (HIPAA) and the European Union's General Data Protection Regulation (GDPR) compliant. Only members of the research team (PI, Co-PIs, biostatistician, research assistant) will have access to the data.

The Stanford research team will use Stanford encrypted, password protected, and backed up electronic devices (laptops, mobile devices) for this project.

d) Describe how data or specimens will be labeled (e.g. name, medical record number, study number, linked coding system) or de-identified. If you are de-identifying data or specimens, who will be responsible for the de-identification? If x-rays or other digital images are used, explain how and by whom the images will be de-identified.

Each participant will be assigned a unique study ID number that will take the place of any identifying information. Surveys will be done online with individual survey URLs matched to study ID provided to participants. All data therefore will be coded for the large dataset.

No names will be attached to surveys. Study staff is responsible for the coding.

Woebot user data provided to Stanford will be de-identified and linked via study ID to the study assessments we collect via RedCap or Qualtrics and the data will not be shared outside of the Woebot and Stanford teams.

e) Indicate who will have access to the data or specimens (e.g., research team, sponsors, consultants) and describe levels of access control (e.g., restricted access for certain persons or groups, access to linked data or specimens).

The PD and co-investigator and the research team will have access to the study data. All data will be locked or password-protected or both.

f) If data or specimens will be coded, describe the method in which they will be coded so that study participants' identities cannot be readily ascertained from the code.

Each participant will be assigned a unique participant ID number, starting with 001 through 1000, to code data.

g) If data or specimens will be coded, indicate who will maintain the key to the code and describe how it will be protected against unauthorized access.

The codes of names and ID numbers will be accessed by the research team only, stored securely in Qualtrics or REDCap, and/or a password protected file.

h) If you will be sharing data with others, describe how data will be transferred (e.g., courier, mail) or transmitted (e.g., file transfer software, file sharing, email). If transmitted via electronic networks, describe how you will secure the data while in transit. See <http://www.stanford.edu/group/security/securecomputing/> <http://www.stanford.edu/group/security/securecomputing/>. Additionally, if you will be using or sharing PHI see <https://uit.stanford.edu/security/hipaa> <https://uit.stanford.edu/security/hipaa>.

Coded data may be sent by secure email settings provided by Stanford.

Title : Woebot for Substance Use Disorders during COVID-19 (SU sIRB)
Approval Period: 04/30/2022 - 04/30/2023

Woebot user data provided to Stanford will be coded and linked via study ID to the study assessments we collect via RedCap or Qualtrics and the data will not be shared outside of the Woebot and Stanford teams.

i) **How will you educate research staff to ensure they take appropriate measures to protect the privacy of participants and the confidentiality of data or specimens collected (e.g. conscious of oral and written communications, conducting insurance billing, and maintaining paper and electronic data)?**

The research staff will all be HIPAA and CITI trained and compliant and supervised by [name].

12. Potential Conflict of Interest

Investigators are required to disclose any financial interests that "<https://researchcompliance.stanford.edu/eprotocol-coi>" target="_blank" reasonably appear to be related/li to this protocol.

Financial Interest Tasks

Investigators	Role	Potential COI?	Date Financial Interest Answered	Date OPACS Disclosure Submitted	COI Review Determination
[REDACTED]	[REDACTED]	[REDACTED]	[REDACTED]		[REDACTED]
[REDACTED]	[REDACTED]	[REDACTED]	[REDACTED]		[REDACTED]

13. Consent Background

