Updated consent forms and HIPAA authorization will be uploaded before the start of recruitment. Ads, questionnaires, etc. will be uploaded for review before recruitment begins.

Recruitment will be a joint effort by Stanford University and Woebot Labs. Woebot will communicate the research opportunity through social media channels. The Stanford team will recruit through listservs and contact participants from previous research studies who are interested in future studies. Working with [name] research team at Stanford, the Woebot team will take part in mapping out message development for the intervention and Woebot's IT team will lead the app programming (including build and quality control/de-bugging). Woebot will collect user data via the Woebot app (automatic process), which

Title : Woebot for Substance Use Disorders during COVID-19 (SU sIRB)
Approval Period: 04/30/2022 - 04/30/2023

will be provided to the Stanford team. The Woebot team will participate in disseminating the study findings via publications and presentations. Participants from recruitment channels will go through and eligibility screener and if eligible, will be asked to use the W-SUDS for 8 weeks and answer a couple of questionnaires administered at the beginning and end of the 8 week period. The data from the questionnaires and app usage during the 8-week period will be analyzed to inform the next study. Woebot will rely on Stanford University IRB for review of this study.

The Stanford team will lead the study evaluations including the study measures, data collection (baseline and follow-ups at the 4- and 8- week marks), data analyses, and writing up of study findings for dissemination. Participants will be randomized to condition after completion via the online assessment platform, which has the functionality to allow randomization to one of two webpages. Those randomized to W-SUDs or WL will see a private, study-only Woebot website or the WL website, respectively. Only then will participants randomized to W-SUDs be informed of Woebot in order to avoid contamination. The WL group has no intervention during the 8-week period and the team will monitor for any intervention usage.

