Participants and Recruitment: N=160 (nationally) will be invited to participate in this study. Recruitment channels may include Woebot Labs' social media avenues (e.g., Facebook, Twitter, LinkedIn, Woebot.io, Nextdoor), Craigslist, Reddit, physical flyers, emailing clinics (with their permission), posting to Stanford Staffers listserv, and advertising to the WELL cohort. Stanford staff may post in other listservs with permission, and contact participants from other studies if those participants have interest in other studies. The team may use Qualtrics panels to recruit. Participants will be entered into the study on a rolling basis. Neither election or declining to participate in the study will impact Woebot users ability to continue using the product as they wish. Inclusion criteria include: all genders aged 18-65 years, access to Woebot on smartphone, be available and committed to engage with app and complete assessments, be willing to provide email address (as this is how assessment incentives will be distributed), and be literate in English (as W-SUDs conversational and video materials will be in English).

Exclusion criteria include: pregnancy (as W-SUDs will not be specifically developed to address the unique needs of this population), history of severe drug/alcohol use, opioid misuse without medication-assisted treatment, and suicide attempt or opioid overdose within the past year. Participants residing outside the U.S. will not be included. Participants who have ever used Woebot will also not be recruited. Use of Woebot (without SUDs program) post randomization, regardless of group assignment, is allowed. Those who elect to participate will be provided with a specific code to enter into Woebot to cue the SUDs specific content.

Randomization: Randomized controlled trial of W-SUDs vs a wait-list control condition (will get access to the SUD program at the end of the study; no intervention during the 8 week period)

This supplemental study proposes to randomize individuals to two conditions (estimating n=80 in each group), W-SUDs or a wait-list control condition, in order to:

- (i) compare between group substance use outcomes at end-of-treatment;
- (ii) assess and analyze comparative impact of Covid-19 in each group;
- (iii) conduct a moderation analysis. Do putative moderators moderate treatment impact upon substance use outcomes?

Primary aim / outcome: Compare between group treatment outcomes.

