Hypothesis: W-SUDs will have significantly improved outcomes compared to the wait-list control group.

Variable of interest: AUDIT/DAST scores across the two groups.

Secondary aim / outcome: Investigate the differential impact of Covid-19 upon psychological functioning across the two groups (one in W-SUDs, the other without intervention).

Purpose: to understand the impact of Covid-19 under a no intervention vs W-SUDs intervention.

Variables of interest: see list below. These variables will be measured at BL, week 4, and end-of-treatment at week 8. Total of 3 surveys.

Exploratory aim / outcome: To investigate putative moderators of treatment on outcome (and/or of treatment engagement).

Variables of interest include:

Mood: depression (PHQ), anxiety (GAD), loneliness, grief

Covid-19 related situational triggers: financial worry, ability to work, essential worker status, safety at home, children at home, degree of closeness to the illness (know someone who is ill, died),

Title : Woebot for Substance Use Disorders during COVID-19 (SU sIRB)
Approval Period: 04/30/2022 - 04/30/2023

Current treatment engagement: level of engagement in other recovery support systems, alliance to Woebot.

Intervention Delivery: W-SUDs will be administered over the course of 8-weeks. Woebot may follow up by email to encourage participants to open the app and check in. The control group will not have access to the W-SUDs program till after completion of their EOT survey at the 8-week mark. Additionally, while the wait-listed group won't have additional surveys (i.e., post app use), we will gather/analyze the info we get from their use of Woebot.

Survey Administration Plan: Qualtrics or REDCap, HIPAA compliant online data center survey administration tools (commonly used by Stanford University), will be utilized to administer the assessment batteries including BL, 4-week, and the EOT questionnaires. During the consent form section, participants will be asked for their email in order to receive study communications including 1) Their signed consent form, 2) Instructions for downloading the Woebot app and using the referral code for the Woebot-SUDs program, and 3) A survey link for follow up assessments. After the baseline is completed, participants will be emailed their signed consent form and instructions. After the 4-week and 8-week phase, participants will receive their survey links via email.

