indicated interest in other studies. The team may use Qualtrics panels to recruit. Woebot exchanges an average of 1-2 million messages per week with its users. Woebot users have indicated interest in substance use content. Specifically, 63% of current users (surveyed in July 2018) reported interest in content related to substance use. In regards to their specific substance use behaviors over the previous month, 22% of users reported having 5 or more alcoholic drinks in a row within a couple of hours (i.e., binge use), and 5% endorsed using non-prescription drugs. Woebot Labs has used these channels for previous research participation invitations with success.

Minor editing changes may be made to recruitment materials to enhance clarity.

Participants will be asked for their age during the screener. If ineligible, they will be not be able to participate in the Woebot for Substance Use Disorders study. We will ask for date of birth in the questionnaire after the signed consent to confirm that the participant is not underage. This is standard best practice for use of the program and for other online research studies.

h) Inclusion and Exclusion Criteria.

Identify inclusion criteria.

Inclusion Criteria:

Eligible participants for this trial must:

1. Have a smartphone
2. Endorse a substance use concern
3. Be between 18 and 65 years of age
4. Be available and committed to engage with the Woebot app
5. Be literate in English.(This is required for inclusion because all materials for app and website will be in English).

Identify exclusion criteria.

Exclusion Criteria:

1. Pregnancy (as W-SUDs will not be specifically developed to address the unique needs of this population)
2. Suicide attempt within the past year (12 months)
3. Symptoms of severe drug/alcohol history: History of delirium tremens; Experiencing hypertension, drenching sweats, seizures or confusion after stopping alcohol or drugs; Liver trouble (cirrhosis or hepatitis); Convulsions or GI bleeding due to drug/alcohol use
4. Opioid overdose within the past year (12 months)
5. Opioid misuse without medication-assisted treatment
6. Not residing in the U.S.
7. Ever used Woebot

i) Describe your screening procedures, including how qualifying laboratory values will be obtained. If you are collecting personal health information prior to enrollment (e.g., telephone screening), please request a waiver of authorization for recruitment (in section 15).

Screening

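### Alliance to Woebot is listed as a moderator of the W-SUDs effect, but it arises only after randomisation and almost only in the W-SUDs arm, so its interaction with arm cannot be identified

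*Protocol*

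**What the plan says.** Protocol section 8(a) sets out three purposes for the randomised comparison. The third is a moderation analysis: "Do putative moderators moderate treatment impact upon substance use outcomes". The exploratory aim in the same section reads "Exploratory aim / outcome: To investigate putative moderators of treatment on outcome (and/or of treatment engagement"), and the variables listed under it include "Current treatment engagement: level of engagement in other recovery support systems, alliance to Woebot".

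The secondary aim, just above, compares the groups on psychological functioning. It names no variables of its own but says "Variables of interest: see list below", and adds "These variables will be measured at BL, week 4, and end-of-treatment at week 8". The only list that follows is the one containing alliance, so alliance appears to inherit both the three-survey schedule and the between-group comparison.

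Three other provisions determine who can have an alliance score:

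- Eligibility, section 8(a): "Participants who have ever used Woebot will also not be recruited". The exclusion lists in 8(b) and 8(h) repeat this ("Ever used Woebot").
- Section 2(a): Woebot is disclosed after randomisation, and only to those assigned to W-SUDs. For the controls, "The WL group has no intervention during the 8-week period and the team will monitor for any intervention usage".
- Section 8(a): the wait-list receives W-SUDs after its week-8 survey and completes no survey after using the app. Generic Woebot, without the substance use program, is allowed in either arm after randomisation.

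The SAP reports that two wait-list participants (2%) downloaded generic Woebot. It describes no moderation model and does not mention alliance.

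**The concern.** A moderator of a randomised effect has to take values in both arms, and it should be fixed before assignment so that the treatment cannot influence it. Alliance meets neither condition. Nobody has a relationship with Woebot at baseline, and later the relationship exists almost only where the app was assigned and used.

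The practical risk is one of interpretation. Software given an arm-by-alliance term will usually drop the redundant column and still print a coefficient. That coefficient could be read as showing that W-SUDs works better in people with a strong alliance. It could equally arise because participants who are more motivated, or who are already improving, rate the bot more highly, while the effect of W-SUDs is the same for everyone.

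**Working it through.** The documents give no sample size, power or precision for the moderation analysis, so there is no stated figure to reproduce. The check has two parts: whether the interaction is identified, and what the two wait-list downloads could add.

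**Inputs.** From the protocol: 80 planned per group. From the SAP: 152 of 180 completed the end-of-treatment survey, 17 treatment participants were lost, and 2 wait-list participants downloaded generic Woebot. Wait-list losses follow as 180 − 152 − 17 = 11. The split of the 180 by arm is not given. Assuming 90 and 90, completers are 90 − 17 = 73 and 90 − 11 = 79.

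**Identification.** Let T be arm (1 = W-SUDs) and A be alliance. A moderation model has four columns: 1, T, A and T×A.

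| Case | What happens to the columns | Rank |
|---|---|---|
| Baseline, no prior exposure, A recorded as any constant c | A = c·1 and T×A = c·T | 2 of 4 |
| Week 4 or 8, wait-list coded 0 | A = 0 whenever T = 0, so T×A = A | 3 of 4 |
| Week 4 or 8, wait-list missing | T = 1 for all remaining rows, so T = 1 and T×A = A | 2 of 4 |

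The interaction is not identified in any of these cases. In the second, the model that can be fitted is b0 + b1·T + b2·A. Because A is 0 for every control, b2 is the slope of outcome on alliance within the W-SUDs arm; the controls contribute only to the residual variance. In the third case there is no control arm left to contrast.

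**Two wait-list scores.** Suppose both downloaders supplied an alliance score. The interaction is the difference between two within-arm slopes. In units of SD(outcome)/SD(alliance), with equal SDs in the arms, approximately

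SE = √[1/(n_T − 1) + 1/(n_W − 1)].

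The detectable interaction at two-sided 5% and 80% power (both assumed) is (1.960 + 0.842) × SE.

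| n_T | n_W | SE | Detectable interaction |
|---|---|---|---|
| 80 | 80 | √(1/79 + 1/79) = 0.159 | 0.45 |
| 80 | 2 | √(1/79 + 1/1) = 1.006 | 2.82 |
| 73 | 79 | √(1/72 + 1/78) = 0.163 | 0.46 |
| 73 | 2 | √(1/72 + 1/1) = 1.007 | 2.82 |

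For scale, a standardised slope is a correlation and lies between −1 and 1, so two such slopes can differ by at most 2. A detectable difference of 2.82 is outside that range. The two scores would also describe generic Woebot rather than W-SUDs, so the two slopes would not be for the same quantity.

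**The case against.** The strongest reply is that the plan does less than this criticism supposes. Four parts of it stand.

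- A reader might infer that the wait-list never uses Woebot. The documents do not support that: generic use is allowed, two participants downloaded it, and W-SUDs is offered after week 8. What holds is no W-SUDs exposure before the week-8 survey and almost no Woebot exposure.
- A reader might infer that alliance has no legitimate use under this aim. The exploratory aim also covers treatment engagement, and alliance sits under an engagement heading. Relating alliance to engagement needs no control values and can be done within the W-SUDs arm. That does not rescue the question about substance use outcomes.
- A baseline alliance measure is inferred. The schedule is written under the secondary aim and reaches alliance only through the pointer to the list. No alliance instrument is named, and this may be loose drafting of a shared list.
- A reader might infer that the trial will report a false moderation result. The SAP contains no moderation model and no rule coding wait-list alliance as 0. Its nearest analysis, of treatment participants' app-use metrics, is already framed as association.

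For the same reason, a simulated false-positive rate should not be attached to this point. With 73 W-SUDs completers and assumed correlations of 0.1, 0.2, 0.3 and 0.4 between alliance and change, a 5% test rejects in roughly 13%, 39%, 73% and 94% of trials. These figures are only the power of a within-arm correlation test, and they rest on an assumed 90/90 split and assumed correlations. They show how readily a within-arm association would appear, not how often this trial would err.

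**Conclusion.** The point holds for moderation of the between-arm effect on substance use. Alliance has no meaningful baseline value, arises after randomisation as a consequence of assignment to W-SUDs, and is almost absent in controls. Its interaction with arm is not identified if the wait-list is coded 0 or left missing. With two scores on a different product it is formally estimable but uninformative.

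The identification result follows from the eligibility, disclosure and access rules and needs no numerical assumption. The precision figures assume equal SDs, two-sided 5%, 80% power, and that both downloaders supplied scores. The results hardly change between 80 and 73 in the W-SUDs arm.

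The consequence is limited to one variable in an exploratory aim. The primary comparison and the other listed moderators are not affected by this point. The documents do not show that such an analysis was run or reported.

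**What to change.** Remove alliance to Woebot from the moderators of the W-SUDs versus wait-list effect, and from any baseline or between-group comparison implied by the secondary aim's pointer.

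Analyse whatever week-4 and week-8 alliance scores were already collected within the W-SUDs arm only, against engagement or change in substance use. Adjust for the baseline substance use score, and for the week-4 score if one is available; the schedule is not explicitly attached to AUDIT and DAST, and the SAP uses only baseline to end-of-treatment change. Label the result as association. Restrict moderation tests to variables that both arms have before randomisation.

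The cost is a wording change to the exploratory aim and one added sentence in the SAP. No new data are needed, and none could be collected: the continuing-review section of the protocol says all participants have completed the interventions and only data analysis remains. The downside is that one intended moderator claim is given up.
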